6.9 Radiation Adverse Events

Adverse Events will be categorized and graded based primarily on the Common Toxicity Criteria for adverse events Version 4.0 (CTCAE version 4.0) with the exception of changes in pulmonary function tests (see section 6.9.4 below).

Radiotherapy should be interrupted for Grade 4 in-field toxicity and resumed when that toxicity has decreased to Grade ≤ 2 as detailed below. If treatment is interrupted for > two weeks, the patient should be removed from study treatment.

6.9.1 Reversible or permanent alopecia, bone marrow toxicity, skin pigmentation, and esophagitis are expected side effects of radiation therapy. Radiation induced myocarditis or transverse myelitis rarely occur at doses lower than 50 Gy. Radiographic evidence of radiation change and subsequent fibrosis of the lung will occur within lung volume receiving ≥20 Gy, usually within the first six months after initiation of treatment. It is essential to spare as much normal lung as possible in order to avoid symptomatic lung injury.

Adverse Event Monitoring

Adverse event data collection and reporting, which are required as part of every clinical trial, are done to ensure the safety of subjects enrolled in the studies as well as those who will enroll in future studies. Adverse events are reported in a routine manner at scheduled times during a trial. Additionally, certain adverse events must be reported in an expedited manner to allow for optimal monitoring of subject safety and care.

All subjects experiencing an adverse event, regardless of its relationship to study therapy, will be monitored until:

- the adverse event resolves or the symptoms or signs that constitute the adverse event return to baseline or is stable in the opinion of the investigator;
- > there is a satisfactory explanation other than the study therapy for the changes observed; or
- death.

Definitions

An adverse event is defined as any untoward or unfavorable medical occurrence in a human research study participant, including any abnormal sign (for example, abnormal physical exam, imaging finding or clinically significant laboratory finding), symptom, clinical event, or disease, temporarily associated with the subject's participation in the research, whether or not it is considered related to the subject's participation in the research.

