FEV-1 Decline	0.90-0.75 times the patient's baseline value	<0.75-0.50 times the patient's baseline value	<0.50-0.25 times the patient's baseline value	<0.25 times the patient's baseline value	Death
Forced Vital Capacity Decline	0.90-0.75 times the patient's baseline value	<0.75-0.50 times the patient's baseline value	<0.50-0.25 times the patient's baseline value	<0.25 times the patient's baseline value	Death
DLCO Decline	0.90-0.75 times the patient's baseline value	<0.75-0.50 times the patient's baseline value	<0.50-0.25 times the patient's baseline value	<0.25 times the patient's baseline value	Death

6.10 Steps to Determine If a Serious Adverse Event Requires Expedited Reporting to the SCCC DSMC and/or HRPP

Step 1: Identify the type of adverse event using the NCI Common Terminology Criteria for Adverse Events (CTCAE v4).

Step 2: Grade the adverse event using the NCI CTCAE v4.

Step 3: Determine whether the adverse event is related to the protocol therapy. Attribution categories are as follows:

- Definite The AE is clearly related to the study treatment.
- Probable The AE is likely related to the study treatment.
- Possible The AE *may be related* to the study treatment.
- Unlikely The AE may NOT be related to the study treatment.
- Unrelated The AE is clearly NOT related to the study treatment.

Note: This includes all events to the end of the acute adverse events reporting period as defined in section 6.9.1. Any event that occurs during the late adverse event period as defined in section 6.9.1 and is attributed (possibly, probably, or definitely) to the agent(s) must also be reported as indicated in the sections below.

Step 4: Determine the prior experience of the adverse event. Expected events are those that have been previously identified as resulting from administration of the treatment. An adverse event is considered unexpected, for expedited reporting purposes only, when either the type of event or the severity of the event is not listed in:

- the current known adverse events listed in the Agent Information Section of this protocol (if applicable);
- the drug package insert (if applicable);
- the current Investigator's Brochure (if applicable)
- the Study Agent(s)/Therapy(ies) Background and Associated Known Toxicities section of this protocol

6.11 Reporting SAEs and UPIRSOs to the Simmons Comprehensive Cancer Center (SCCC) Data Safety Monitoring Committee (DSMC)

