7.0 Drug Therapy

At the treating physician's discretion, chemotherapy may be administered concurrently ONLY to patients enrolled on the standard arm (30 fractions) using a combination of carboplatin and paclitaxel (Taxol) with standard dosing for concurrent chemo-radiotherapy in lung cancer. Patients treated on this arm, however, may not receive any other chemotherapy regimens, targeted therapy, or drugs known to act as radiosensitizers. Patients on the experimental arm (15 fractions) may NOT receive any concurrent chemotherapy, targeted therapy or drugs known to act as radiosensisitizers. Patients on either arm of the study may go on to receive adjuvant chemotherapy if determined appropriate by their medical oncologist one week after completing radiation therapy.

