9.2 Criteria for Toxicity

All acute and late adverse events from protocol radiation therapy will be reported and scored for severity using the NCI Common Terminology Criteria for Adverse Events (CTCAE) version 4.0. A copy of the CTCAE v4.0 can be downloaded from the CTEP home page (http://ctep.info.nih.gov).

Please note that this study will not be using separate toxicity scales for acute and late radiation adverse events.

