11.1.2.4 Toxicity: Grade 3-5 adverse events as graded by CTCAE v 4.0

11.2 Sample Size Determination

The sample size calculation is based on the primary endpoint, overall survival at 1 year, and the assumption that patients are randomized until the end of accrual. The sample size is calculated with the 2-sided significance level of 0.05 and 80% statistical power using a 2-sample log rank test. We assume that the overall survival function follows an exponential distribution for each arm. Accrual to the study is assumed to be uniformly distributed. The null hypothesis is that the there are no difference in 1-year survival rates between two arms. We assume that the patients will be accrued for 2 years with a 1-year follow-up. We hypothesize that the patients randomly assigned to the control arm and experimental arm have a 1-year survival rate of 45% (hazard rate [λc]) of 0.799) and 60% (hazard rate [λe]) of 0.511), respectively, which is translated to the hazard ratio of $\lambda e/\lambda c = 0.640$. One interim analysis and a final analysis are planned for early stopping for efficacy. The efficacy testing is based on the Lan-DeMets spending function, which resembles the O'Brien-Fleming boundary. The total sample size of 226 patients (113 in the control arm and 113 in the experimental arm) will be accrued to achieve the desired 80% statistical power and 2-sided significance level of 0.05. Guarding against ineligibility or lack-ofdata rate of up to 5%, the final targeted accrual for this study will be 238 patients (119 per arm). Sample size was estimated using the sample size software EaST version 5.

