11.5.7 Toxicity

Any subject who receives treatment on this protocol will be evaluable for toxicity. Each patient will be assessed for the development of toxicity according to the Time and Events table (Appendix II). Toxicity will be assessed according to the NCI Common Toxicity Criteria for Adverse Events (CTCAE), version 4.0. Dose adjustments should be made according to the system showing the greatest degree of toxicity.

Only adverse events assessed to be definitely, probably, or possibly related to protocol treatment will be considered. The rates of all Grade 3-5 adverse events, and death during or within 30 days of discontinuation of protocol treatment will be tested for equality using a two-sided chi-square test with a 0.05 significance level.

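### The toxicity endpoint is all Grade 3-5 adverse events, but the test counts only events judged treatment-related, and the plan does not say whether Arm B chemotherapy events count

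*Combined protocol and SAP*

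**What the plan says.** Toxicity is a secondary objective (2.2.1), and the endpoint list in 11.1.2.4 reads "Toxicity: Grade 3-5 adverse events as graded by CTCAE v 4.0". It has no relatedness condition.

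The analysis section, 11.5.7, adds one: "Only adverse events assessed to be definitely, probably, or possibly related to protocol treatment will be considered". The next sentence nevertheless refers to the rates of all Grade 3-5 events, together with "death during or within 30 days of discontinuation of protocol treatment", and says that these "will be tested for equality using a two-sided chi-square test with a 0.05 significance level". Section 11 plans no comparison without the filter.

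Three other places bear on what the filter lets through:

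- Section 6.10, step 3: "Determine whether the adverse event is related to the protocol therapy". It gives five categories, from definite to unrelated. It does not say who assigns them, or that the assessor is masked or central.
- Section 9.2: "All acute and late adverse events from protocol radiation therapy will be reported and scored for severity".
- Section 7.0: "chemotherapy may be administered concurrently ONLY to patients enrolled on the standard arm (30 fractions" and so on, limited to carboplatin and paclitaxel at the treating physician's discretion.

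Follow-up of events is wider than the test. Section 6.9.1 says: "All subjects experiencing an adverse event, regardless of its relationship to study therapy, will be monitored until" resolution or another listed end point.

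**The concern.** There are two linked problems.

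**The tested quantity is not the stated endpoint.** A Grade 3-5 event enters the 11.5.7 test only if someone calls it at least possibly related. In this population that call is hard. Patients qualify through poor performance status, weight loss or unfitness for combined treatment (3.1.4), and comorbidity is expected (9.7). The call is also made, in effect, with knowledge of the arm. Section 9.9 itself says that hypofractionation may raise normal tissue toxicity, an expectation that could colour attribution. If the share of events called related differs by arm, the test can show a difference that attribution created, or hide a real one.

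**The reference treatment for relatedness is unclear in Arm B.** Section 1.4 says concurrent chemotherapy was first prohibited and then allowed by amendment, in the standard arm only. The attribution wording does not mention it. Section 11.5.7 refers to *protocol treatment*, a term that 6.1 and 6.2 use in the radiation sections, and 9.2 refers to radiation alone. One site could count chemotherapy-induced neutropenia and another could drop it. Section 1.1 accepts that adding chemotherapy raises toxicity, so these events may not be few. Dropping them would understate toxicity in the control arm only.

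**Working it through.** **The plan's own figure.** The toxicity test has no stated rates, power or detectable difference, so there is no figure to reproduce. The only sizing is for overall survival. It reproduces (158 events / mean event probability 0.700 = 225.8, so 226; 226 / 0.95 = 237.9, so 238) and serves here only to supply 119 patients per arm.

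**Method.** Assume the same all-cause Grade 3-5 rate in both arms. Then:

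related rate in an arm = all-cause rate × share of events called related

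The rejection probability is the sum, over all pairs of binomial counts (x1, x2) with n = 119 per arm, of the probability of each pair for which

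(x1/n − x2/n)² / [2p̄(1 − p̄)/n] > 3.84, where p̄ = (x1 + x2)/(2n).

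This is the two-sided 0.05 chi-square test without continuity correction. The attribution shares are assumptions: 60% in one arm and 70-80% in the other. No direction is assumed.

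| All-cause rate, both arms | Shares called related | Related rates tested | Test rejects |
|---|---|---|---|
| 10% | 60% vs 70% | 6% vs 7% | 6% |
| 10% | 60% vs 80% | 6% vs 8% | 10% |
| 15% | 60% vs 80% | 9% vs 12% | 12% |
| 30% | 60% vs 70% | 18% vs 21% | 9% |
| 40% | 60% vs 70% | 24% vs 28% | 11% |
| 40% | 60% vs 80% | 24% vs 32% | 28% |
| 50% | 60% vs 80% | 30% vs 40% | 37% |

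With equal shares the test rejects about 5%. With 113 per arm the 40% rows give 11% and 27%. A different assumed pair, 90% vs 70% at 113 per arm by normal approximation, gives 13%, 18%, 25% and 34% at all-cause rates of 20%, 30%, 40% and 50%.

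**Which rows are plausible.** Section 1.2 gives one anchor from the earlier dose-escalation trial: 4 patients with Grade 3 or higher treatment-related toxicity among 52 enrolled. That is 4/52 = 7.7%. The dose-level counts given there sum to 18 + 23 + 21 = 62, which would make it 4/62 = 6.5%. This points to the upper rows. Section 6.9.2, however, expects a significant portion of patients to have Grade 3 esophagitis, which points lower in the table. The documents do not settle it.

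**Chemotherapy events, illustration only.** Assume radiation-related Grade 3-5 toxicity of 15% in both arms, half of Arm B receiving chemotherapy, and a 20-40% added risk of a chemotherapy-only Grade 3-5 event in those patients who would otherwise have none. If these events count, the Arm B rate is

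0.15 + 0.85 × 0.5 × 0.20 = 23.5%, up to 0.15 + 0.85 × 0.5 × 0.40 = 32%.

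With 113 per arm, the test against 15% rejects 37% to 86% of the time. If the events are left out as unrelated, both arms show 15% and it rejects 5%. The same data can therefore give different conclusions depending on how one undefined term is read.

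**The case against.** The strongest reply is that the filter is wide. Events called possibly related count, and only the unlikely and unrelated categories drop out, so a gap of 10-20 percentage points must arise at one boundary. That softens the problem. It does not remove it, because the boundary between possible and unlikely is where judgement matters most.

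Second, the larger rejection figures rest on assumed rates. At related rates near those of the earlier trial, the excess over 5% is small. This stands, and it is why the size is given as a range.

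Third, a reader might infer that the plan excludes chemotherapy toxicity. The documents do not support that. Section 11.5.7 says protocol treatment, and carboplatin/paclitaxel is the one concurrent regimen that 7.0 permits. Section 6.10 mentions agents and package inserts where applicable. Reading the term to include these drugs is natural. What stands is that the term is undefined and that 9.2 is narrower.

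A reader might also infer that the documents name an unblinded investigator as the assessor. They do not name an assessor or use the term open-label. Awareness of arm is inferred from the regimens and from the absence of any masking.

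Finally, attribution does not govern every safety result. Overall survival counts all deaths, and the deaths within 30 days in 11.5.7 may be tested regardless of cause, though the wording is unclear. Neither covers non-fatal Grade 3-4 events.

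**Conclusion.** The point holds as an inconsistency between the endpoint definition (11.1.2.4) and its analysis (11.5.7), with an undefined attribution scope that matters only in Arm B. The primary analysis is not affected.

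The size is unknown. Under the assumed differential attribution, the rejection rate with equal true toxicity runs from near nominal to several times nominal across the rates examined. It would be too strong to say that the toxicity result will be biased, or in which direction: the documents give neither attribution shares nor all-cause rates. It would also be too strong to say that the all-cause test must replace the related-only one. Both are informative, and the choice of lead analysis is partly preference. The supportable conclusion is that the comparison matching the stated endpoint is missing and should be added.

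**What to change.** 1. In 11.5.7, add a comparison by arm of all Grade 3-5 adverse events regardless of attribution, matching 11.1.2.4, and report it beside the related-only comparison. Say whether the relatedness condition applies to the 30-day deaths.
2. State in 11.5.7 that carboplatin/paclitaxel given in Arm B as 7.0 permits counts as protocol treatment for attribution, and bring 9.2 into line so that reporting is not confined to radiation events.
3. Note the limit on the all-cause comparison: under 6.9.1, late events are taken only from Radiation Oncology visits, so events seen elsewhere may be missed.

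The cost is a few sentences and one extra table. Because 6.9.1 follows events regardless of relationship, the data should largely exist, but check that sites have not recorded only radiation events under 9.2. The statistical price is dilution: background illness adds events to both arms and can blur a real treatment difference, which is a reason to keep the related-only rates alongside.

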The best method found to date for improving the efficacy of radiation therapy for locally advanced NSCLC is to combine it with chemotherapy. One of the early phase III trials showing a benefit to chemotherapy followed by radiation therapy was the CALGB 8433 trial, which showed a median survival increase from 9.6 to 13.7 months with the addition of chemotherapy [7]. Since then, multiple trials of locally advanced NSCLC in good performance status patients have shown even better outcomes with concurrent chemotherapy and radiation therapy, rather than sequential [8-12]. A recent randomized phase III trial even achieved a median survival time of 21.7 months in inoperable stage III NSCLC [13].

However, the better local control and survival achievable by adding chemotherapy to radiation therapy comes at the expense of increased toxicity. Some of the most commonly used chemotherapy combinations in locally advanced NSCLC are cisplatin/etoposide and carboplatin/paclitaxel. All of these agents are associated with myelosuppression, nausea, and vomiting and several are associated with neuropathy and nephrotoxicity. When given with radiation therapy, these toxic effects can be worsened and the adverse effects commonly seen with radiation therapy to the chest, such as esophagitis, can be intensified. The CALGB 8433 trial reported higher rates of serious adverse effects including neutropenic infections, vomiting, and severe weight loss in the group of patients receiving chemotherapy and radiation therapy [14]. Toxicity with concurrent chemoradiation therapy can be even greater than with sequential. RTOG 94-10 reported higher rates of acute grade 3-4 non-hematologic toxicity, including esophagitis, with concurrent compared to sequential chemoradiation therapy [9]. In a phase III trial by the CALGB and ECOG, patients receiving carboplatin with radiation therapy suffered more neutropenia, thrombopenia, and anemia than did patients receiving radiation therapy alone [15]. These adverse effects can decrease quality of life for patients and cause administration of combined modality therapy to be impractical in poor performance status patients.

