9.9 Health-Related Quality of Life (HRQOL) Analysis

The study design is to prospectively analyze the QOL among patients with stage III NSCLC randomized between standard radiotherapy (60 Gy) versus hypofractionated IGRT radiation therapy. While hypofractionation is hypothesized to yield greater tumor cell kill, it may also increase the normal tissue toxicity, in which case there may be a decrease in HRQOL. The primary normal tissue toxicities in patients receiving radiation for lung cancer are esophagitis and pneumonitis. Prior studies have demonstrated that the most sensitive and clinically meaningful method for accurately capturing the normal tissue toxicities is via patients reported outcomes (PROs), such as HRQOL.

In this randomized trial, we plan to assess the FACT-TOI in all arms at 4 specific

time points to minimize patient burden: baseline (pretreatment), at the end of treatment (last day of treatment), and at the 6 and 12 month follow ups (See Appendix II). In order to analyze the difference in QOL between all arms, we plan to use a brief, validated instrument that is user friendly and has clinical relevance (the Lung Cancer Subscale of the FACT-TOI). FACT-TOI is a measure that sums the functional well being (FWB), physical well being (PWB), and the lung cancer subscale (LCS) of the Functional Assessment of Cancer Therapy - Lung (FACT-L) QOL instrument, which has been extensively used for measuring QOL in patients with lung cancer.[31] In a review of the literature reported that the FACT-L scale has been used in more than 5,000 patients and has been found to be sensitive to changes in performance status, treatment response.[32] FACT has been translated into 26 languages and is available free of charge to institutions with the completion of an agreement to share data, accessible at

http://www.facit.org/translation/licensure.aspx. The full FACT-L questionnaire can be completed in less than 10 minutes. This instrument has not only been shown to be prognostic for survival, but also sensitive to changes in QOL on serial evaluations throughout treatment. Importantly, the FACT-TOI has been associated with clinically meaningful changes in

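### Section 11.5.7 pools all related Grade 3-5 events and plans no arm comparison of pneumonitis or esophagitis, so an excess in Arm A can be diluted and, depending on attribution, partly offset by concurrent chemotherapy events in Arm B

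*Combined protocol and SAP*

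**What the plan says.** Section 11.1.2.4 defines the secondary safety endpoint with no split by organ: "Toxicity: Grade 3-5 adverse events as graded by CTCAE v 4.0". Section 11.5.7 gives the comparison: "The rates of all Grade 3-5 adverse events, and death during or within 30 days of discontinuation of protocol treatment will be tested for equality". The method is a chi-square test, two-sided at the 0.05 level. The section also applies a relatedness filter: "Only adverse events assessed to be definitely, probably, or possibly related to protocol treatment will be considered". No comparison by organ or event category is planned anywhere in section 11.

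Section 9.9 says which harms matter most: "The primary normal tissue toxicities in patients receiving radiation for lung cancer are esophagitis and pneumonitis". It adds that hypofractionation may raise normal-tissue toxicity. The dose-limit table in section 6.1.5 is also built on organ-specific Grade 3 or higher endpoints.

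The arms differ in drug exposure during radiation. Section 7.0 permits concurrent carboplatin/paclitaxel in Arm B at the physician's discretion and says "Patients on the experimental arm (15 fractions) may NOT receive any concurrent chemotherapy". Section 1.1 says of the chemotherapy agents in common use, including these two, "All of these agents are associated with myelosuppression, nausea, and vomiting". It also reports more neutropenia, thrombopenia and anemia with carboplatin plus radiation than with radiation alone.

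**The concern.** The safety question for larger fractions is whether Arm A has more severe lung or esophageal injury. The one planned test does not ask that. It asks whether the total of severe related events differs, and two things separate that total from the organ-specific answer.

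- **Dilution.** Severe events that occur equally in both arms raise both rates and shrink the contrast. Section 6.9.2 itself expects Grade 3 esophagitis in a significant share of patients.
- **Offset.** Concurrent chemotherapy can add severe events in Arm B only, which pulls the pooled difference toward zero or below.

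At stake is whether the trial's formal safety comparison can show an increase in the harm that section 9.9 singles out.

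**Working it through.** **1. The plan's own figure.** The plan states no rate or power for toxicity. The only figure it fixes is the number per arm, which comes from survival. One-year survival of 45% and 60% gives hazards −ln 0.45 = 0.799 and −ln 0.60 = 0.511, so HR = 0.640. Events needed = 4(1.960 + 0.842)² / (ln 0.640)² ≈ 158. With 2 years of uniform accrual and 1 year of follow-up, the event probability is 1 − (e^−λ − e^−3λ)/(2λ), which is 0.775 and 0.624, mean 0.700. N = 158/0.700 ≈ 226, or 113 per arm, as stated in section 11.2. I use 113 per arm below.

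**2. Assumptions (none are in the plan).** Grade 3 or higher pneumonitis is 15% in Arm A and 5% in Arm B. Grade 3 or higher esophagitis is 10% in both. Components are independent. Let d be the share of Arm B patients with a Grade 3-5 event caused by concurrent chemotherapy that passes the relatedness filter, so d = uptake × event rate among those treated.

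**3. Pooled rates.**
- Arm A: 1 − (0.85)(0.90) = 23.5%
- Arm B: 1 − (0.95)(0.90)(1 − d)

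**4. Power, two-sided chi-square at 0.05, exact binomial calculation, 113 per arm.**

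| d in Arm B | Example | Pooled A vs B | Power, pooled test |
|---|---|---|---|
| 0 | no concurrent drug events | 23.5% vs 14.5% | 41% |
| 4% | 20% × 20% | 23.5% vs 17.9% | 18% |
| 7.5% | 25% × 30% | 23.5% vs 20.9% | 8% |
| 12% | 40% × 30% | 23.5% vs 24.8% | 6% |

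A separate test of pneumonitis, 15% vs 5%, has 74% power whatever d is. In the last row only 1.5% of trials would reject in the direction of Arm A being worse.

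**5. Where the sign turns.** The pooled rates are equal when 0.85 = 0.95(1 − d), so d = 1 − 0.85/0.95 = 10.5%. Reversal needs more than that.

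**6. How much is due to chemotherapy.** The fall from 74% to 41% occurs at d = 0, from esophagitis alone. Only the fall from 41% downward comes from concurrent drug events.

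**7. Lower rates.** The separate test is also weak when pneumonitis is rarer: 31% power for 6% vs 2%, and 49% for 9% vs 3%.

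**8. Limit on uptake.** Section 11.5.9 says the first 44 patients enrolled before concurrent chemotherapy was allowed. If about 22 of them are in Arm B, at most (113 − 22)/113 = 81% of Arm B could receive it. The expected share is not stated.

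**The case against.** Much can be said for the plan, and several points limit the concern.

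- **Chemotherapy and marrow events are not confined to Arm B.** A reader might infer that they are. Section 3.1.9 allows sequential chemotherapy in either arm, section 7.0 allows adjuvant chemotherapy in either arm, and section 6.9.1 lists bone marrow toxicity as an expected radiation effect. Only events from *concurrent* chemotherapy are specific to Arm B. This stands, but events shared by both arms do not restore the contrast. With an assumed further 10% in each arm, the pooled test has 28% power at d = 0 and 5% at d = 12%.
- **The relatedness filter may remove drug events.** Section 11.5.7 refers to protocol treatment, while section 9.2 has a narrower scope: "All acute and late adverse events from protocol radiation therapy will be reported and scored for severity". If the filter means radiation only, events attributed purely to drugs drop out and the offset largely disappears. The documents do not settle this. A possible relation is enough to count, so low counts during chemoradiation could still pass.
- **The plural in 11.5.7 could mean each event type.** One pooled rate is the likelier reading, not an explicit statement. On the other reading the plan implies an unspecified number of tests with none named, so the text needs rewording either way.
- **Blood counts are scheduled only at baseline (Appendix II).** Asymptomatic hematologic events may therefore be under-recorded, which weakens the offset.
- **The assumed 15% is high against cited experience.** Section 1.2 reports 6% Grade 3 or greater late pulmonary toxicity in one series, Grade 3 pneumonitis in 2 of 30 in another, and 4 patients with any Grade 3 or higher related toxicity in the dose-escalation trial. This stands; hence the lower-rate figures in step 7.
- **Other monitoring exists.** Yearly reports describe adverse events (11.5.8), the DSMC reviews them quarterly (12.4), and FACT-L covers lung symptoms. These make complete concealment unlikely. None is a Grade 3 or higher organ-specific arm comparison, and the yearly reports exclude treatment comparisons on secondary endpoints, of which toxicity is one.

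**Conclusion.** The point holds in a limited form. On its natural reading, 11.5.7 offers one pooled comparison plus early death and no arm comparison of the two toxicities that section 9.9 puts first. Pooling alone costs power: 74% to 41% under the stated assumptions. Concurrent chemotherapy in Arm B can take it lower, to 18%, 8% or 6% when 4%, 7.5% or 12% of Arm B have a qualifying drug event.

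Two stronger readings are not supported. The documents do not show that cancellation will occur, because uptake, drug-event rates and the scope of attribution are all unstated. Nor do they say that a non-significant pooled test would be read as equal toxicity; 11.5.7 specifies a test and is silent on how to interpret it.

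Separate comparisons are no guarantee of detection, given the 31% and 49% power at lower rates. That is why estimates with intervals are preferable to tests alone. The recommendation does not depend on the uptake figure. It is a cheap improvement worth making, not a flaw that invalidates the design.

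**What to change.** In section 11.5.7:

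1. Prespecify arm comparisons, each as a rate difference with 95% CI, of patients with (a) Grade 3 or higher pneumonitis, (b) Grade 3 or higher esophagitis, and (c) any other Grade 3 or higher event of the kinds listed in section 6.1.5.
2. Keep the pooled Grade 3-5 rate as an overall total, say explicitly that it counts patients with at least one such event, and show hematologic events separately.
3. State whether *protocol treatment* includes concurrent chemotherapy for attribution, and reconcile this with section 9.2.
4. Show Arm B by concurrent chemotherapy received as description only, because that split is made after randomization. Note beside the esophagitis result that concurrent chemotherapy can itself intensify esophagitis (section 1.1), so this comparison is still against a mixed Arm B.

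Cost: SAP wording and a few tables from data already collected, with no change to treatment, visits or sample size. The downside is a few extra safety comparisons without multiplicity control, which should be stated when they are reported.
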